5.5 Subject Withdrawal

Subjects may withdraw voluntarily from the study or the investigator may terminate a subject's participation at any time.

5.5.1 Reasons for Withdrawal

Participants are free to withdraw from participation in the study at any time, for any reason, with no explanation upon request. This decision will not interfere or alter in any way their following treatments and pain management if they are patients of the dental school, the Brotman Facial Pain Clinic, the Oral and Maxillofacial Surgery Clinic or the Pain Clinic at the medical school.

If a participant does not return for a scheduled visit, every effort will be made to contact the participant and to document the outcome. If a participant withdraws consent and

refuses to come to an Early Termination Visit, no further evaluations will be performed, and no attempts will be made to collect additional data.

Investigators may withdraw a participant for any of the following reasons:

- Withdrawal of consent
- The participant does not meet eligibility criteria for randomization.
- Any clinical adverse event (AE), laboratory abnormality, or other medical condition or situation occurs such that continued participation in the study would not be in the best interest of the participant.
- The subject meets an exclusion criterion (either newly developed or not previously recognized) that precludes further study participation.
- Pregnancy
- At Investigator discretion

5.5.2 Handling of Subject Withdrawals or Subject Discontinuation of Study Intervention

Participants withdrawn after randomization will not be replaced. Participants who are withdrawn voluntarily or by the investigator will be discontinued from the study.

Study staff will complete a study disposition form in the eCRF, indicating the reason for discontinuation.

If the patient is a patient from the school and/or is interested in following orofacial pain care at the Brotman Facial Pain clinic, will be referred to the faculty practice clinic front desk for information and to schedule an appointment if wants to.

Unblinding, if required, will be carried out according to the procedures described in Section 5.4.2. A participant who has an AE at the time of discontinuation will be followed until the event returns to baseline, resolves, or is stabilized. If the AE does not meet one of these outcomes within 30 days after discontinuation or the end of the study, the participant will be referred to an appropriate provider for continued medical care (See section 9.2).

5.6 Premature Termination or Suspension of Study

This study may be suspended or prematurely terminated if there is sufficient reasonable cause as determined by sponsor the PI, medical monitor, DSMB, or IRB. Written

notification, documenting the reason for study suspension or termination, will be provided by the suspending, or terminating party. If the study is prematurely terminated or suspended, the principal investigator will promptly inform the IRB and will provide the reason(s) for suspension or termination.

Circumstances that may warrant termination include, but are not limited to:

- Determination of unexpected, significant, or unacceptable risk to subjects.
- Insufficient adherence to protocol requirements.
- Data that are not sufficiently complete and/or evaluable.
- Determination of futility.

6 STUDY INTERVENTION

6.1 Study Product Description

The investigational drug is Erenumab-aooe (Aimovig), an FDA approved medication for the prevention of migraine. Erenumab-aooe is a fully human monoclonal antibody IgG2 that binds in a competitive and reversible manner to the Calcitonin Gene Related Peptide (CGRP) receptor. It is available as a subcutaneous injection only and it is used once a month.

Erenumab injection is a sterile, preservative-free, clear to opalescent, colorless to light yellow solution for subcutaneous administration. The needle shield of the prefilled syringes contain dry natural rubber (a derivative of latex). The syringe is a prefilled glass syringe with a stainless-steel needle and delivers 1 mL of 140 mg/mL. Each 1 mL 140 mg single-dose prefilled glass syringe contains 140 mg erenumab-aooe, acetate (2.0 mg), polysorbate 80 (0.10 mg), and sucrose (65 mg).

The placebo injection is a sterile solution. The syringe is a 1 mL prefilled glass syringe of Sodium Acetate, Sucrose, Sucrose, polysorbate 20, pH 5.2

6.1.1 Acquisition

Our study will use Erenumab at the dosage of 140 mg/mL once monthly. The drug will be acquired from AMGEN, the manufacturer, and shipped to the research pharmacy at the University of Maryland. The research pharmacy will release the drug to study personnel, who will dispense it to the participants at study visits. The placebo will be also acquired from AMGEN and will be packaged, labeled, dispensed, and administered in the same manner as described above for the active drug. Placebo ingredients are Sodium Acetate, Sucrose, polysorbate 20, at pH 5.2. Storage requirements for the placebo are the same as for the active drug.

6.1.2 Formulation, Packaging, and Labeling

Erenumab 140 mg, in 1 mL prefilled glass syringe will be used. The syringe is a prefilled glass syringe with a stainless-steel needle and delivers 1 mL of 140 mg/mL. Each 1 mL 140 mg single-dose prefilled glass syringe contains 140 mg erenumab-aooe, acetate (2.0 mg), polysorbate 80 (0.10 mg), and sucrose (65 mg) at pH 5.2. The placebo will be Placebo 1 mL in a prefilled glass syringe consisting of Sodium Acetate, Sucrose, Polysorbate 20, pH 5.2. Neither study personnel nor study participants will be able to differentiate the study drug from placebo by appearance alone.

The research pharmacy will label and dispense the autoinjectors in individual cartons. The cartons will be labeled with the following information:

• Name and address of the dispensing pharmacy

- Protocol number
- Name of the drug labeled as "Erenumab or placebo" to protect the blinding
- Strength of the drug or placebo (140 mg/ml). Dispense 1
- Name of the prescribing clinician
- Instructions for use
- Participant name and clinic record number
- Date dispensed
- The following statement: "Limited by Federal Law to Investigational Use Only"

6.1.3 Product Storage and Stability

Erenumab will be stored following the instructions of the manufacturer. Erenumab needs to be stored refrigerated at 2°C to 8°C (36°F to 46°F) in the original carton to protect from light until time of use.

• If removed from the refrigerator, Erenumab should be kept at room temperature (up to 25°C [77°F]) in the original carton and must be used within 7 days. It will be thrown away if it has been left at room temperature for more than 7 days. It should not be freeze or shaken.

Study personnel will pick up the study product from the research pharmacy the day prior or the same day that will be administered to participants. If picked up a day before to be administered, the study product will be stored in an allocated refrigerator specifically for its storage at the Brotman Facial Pain Clinic.

6.2 Dosage, Preparation and Administration of Study Product

Erenumab 140 mg/mL or placebo prefilled glass syringe will be administered subcutaneously once monthly.

Erenumab or placebo will be administered by the study personnel who will be trained in how to administer it using the single-dose prefilled syringe, including aseptic technique and according to the instructions of the manufacturer.

• Prior to subcutaneous administration, allow Erenumab to sit at room temperature for at least 30 minutes protected from direct sunlight.

- - Do not warm by using a heat source such as hot water or a microwave.
 - Do not shake the product.
 - Inspect visually for particulate matter and discoloration prior to administration [see Dosage]
 - Do not use if the solution is cloudy or discolored or contains flakes or particles.
 - Erenumab or placebo will be administered in the abdomen, thigh, or upper arm subcutaneously.
 - It will not be injected into areas where the skin is tender, bruised, red, or hard.
 - Both prefilled autoinjector and prefilled syringe are single-dose and deliver the entire contents.
 - Erenumab or placebo administration to participants will be once a month for 3 months on Visits 1-3. The study personnel will explain the participant how it will be injected. Participants will receive the first dose on Visit 1. The second dose a month after on Visit 2 and the third and last dose a month after the second dose on Visit 3 for a total of 3 cycles. After administration, the patient will wait 20 minutes in our clinic to make sure there is not any reaction. After the 20 minutes, study personnel will assess, schedule next visit and the patient will be free to leave.
 - Erenumab or placebo is for subcutaneous use only. The needle shields of erenumab and placebo prefilled syringe contain dry natural rubber (a derivative of latex), which may cause allergic reactions in individuals sensitive to latex. Sensitivity to latex is included in the exclusion criteria (See 5.2)

6.3 Modification of Study Product Administration for a Subject

If a dose of Erenumab is missed, will be administered as soon as possible. Thereafter, Erenumab will be scheduled monthly from the date of the last dose.

The safety profile of erenumab has been favorable in clinical trials and in the post-marketing setting. A limited number of adverse drug reactions (injection site reactions, constipation, muscle spasm, and pruritus) have been identified at low frequencies (< 5%) in clinical trials. In the long-term use of erenumab, the safety profile remained consistent through 5 years of open-label treatment. In post-marketing settings, hypersensitivity reactions (including rash, angioedema and anaphylactoid reactions) and constipation with serious complications have been reported. In addition, oral sores (eg, stomatitis, mouth

ulceration, oral mucosal blistering), alopecia and rash (eg, rash papular, exfoliative rash, rash erythematous, urticaria, blister) have been observed in post-marketing surveillance.

Adverse reactions with the use of Erenumab have been hypersensitivity reactions, constipation with serious complications and hypertension. Exclusion criteria includes medical history of constipation or taking medications associated with decrease of G.I motility as well as pre-existent hypertension (See 5.2). If the participant reports a hypersensitivity reaction (rash, angioedema, anaphylaxis), new onset constipation or new onset of hypertension or if the participant decides against using Erenumab, he/she will be discontinued from the study (See 2.3.1 and 5.5.2).

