2.3 Potential Risks and Benefits

2.3.1 Potential Risks

Use of Erenumab: Erenumab is a fully human monoclonal antibody that inhibits CGRP receptor and is FDA approved for the preventive treatment of migraine. As of 16 May 2020, approximately 6,550 people have received erenumab in research studies. Since it was first approved for sale on 17 May 2018, approximately 423,800 people have been prescribed erenumab (Aimovig®) for treatment as of 16 May 2020.

The safety profile of erenumab has been favorable in clinical trials and in the post-marketing setting. A limited number of adverse drug reactions (injection site reactions, constipation, muscle spasm, and pruritus) have been identified at low frequencies (< 5%) in clinical trials. In the long-term use of erenumab, the safety profile remained consistent through 5 years of open-label treatment. In post-marketing settings, hypersensitivity reactions (including rash, angioedema and anaphylactoid reactions) and constipation with serious complications have been reported. In addition, oral sores (eg, stomatitis, mouth ulceration, oral mucosal blistering), alopecia and rash (eg, rash papular, exfoliative rash, rash erythematous, urticaria, blister) have been observed in post-marketing surveillance.

Serious constipation has been reported in patients prescribed erenumab. In some cases, hospitalization or surgery was required. Constipation and the use of medications that decrease gastric motility are in our exclusion criteria, however if a new onset of constipation occurs, the participant will be withdrawn of the study and will be referred to an appropriate practitioner for continued care (see section 9.2).

High blood pressure: High blood pressure or worsening of high blood pressure.

After taking erenumab, antibodies against erenumab may be produced; this has been observed in clinical studies. No side effects associated with these antibodies were observed.

Side effects of the use of erenumab in combination with other drugs are unknown at this time.

There are no adequate data on the developmental risk associated with the use of erenumab in pregnant women or breastfed babies. There are no data on the presence of erenumab in human milk, or on milk production. Pregnant women, breastfeeding women and women planning to become pregnant will be excluded from this study. If a participant

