5.2 Subject Exclusion Criteria

- 1. Participants with a history of congestive heart failure or uncontrolled diabetes.
- 2. Participants with serious hepatic, respiratory, hematologic or immunologic illnesses, an unstable cardiovascular disease, or any other severe acute or chronic medical or psychiatric condition or laboratory abnormality that may increase the risk associated with trial participation or Erenumab or may interfere with the interpretation of trial results and, in the judgment of the investigator, would make the participant inappropriate for entry into this trial.
- 3. Participants with high blood pressure, uncontrolled high blood pressure, malignant disease, chronic constipation, any malabsorption disorders such as IBSc or any other severe acute or chronic medical or psychiatric condition (major depression, schizophrenia, dementia) or laboratory finding that may increase the risk associated with trial participation with Erenumab, that in the judgement of the investigators would interfere with study assessments and/or would make the participant inappropriate for entry into this trial.
- 4. Participants with active malignancy of any type or a history a malignancy (with exception of participants with malignancy surgically removed with no evidence of recurrence within 5 years before enrollment.
- 5. Participants with evidence or a history of drug or alcohol abuse within the past 12 months or has been diagnosed with a substance abuse disorder.
- 6. Participants with dental pain (determined pain of odontogenic/periodontal origin).
- 7. Participants with significant neurological disorders.
- 8. Patients with chronic migraine with and w/o aura following the ICHD-3 criteria treated or not treated with medication
 - Without excluding headache attributed to TMD
- 9. Participants currently taking or have previously taken Erenumab or other CGRP monoclonal antibody (mAmb) or currently taking a CGRP-Receptor antagonist (gepants) for migraine prevention.
- 10. Patients with hypersensitivity to Erenumab
- 11. Participants with trigeminal neuropathic pain taken medications for the management of trigeminal neuropathic pain in where daily dosage has been modified within three weeks before baseline.

- 12. Neuroimaging showing the presence of neurovascular compression or AV malformation.13. Neuroimaging showing the presence of intracranial pathology (i.e. multiple sclerosis, tumor).
- 14. Presence of extracranial pathology in the area of pain (tumor, lesion).

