- 15. Has been treated with another investigational drug or treatment within 30 days prior to the Screening and Baseline Visit
- 16. Has commenced a new daily prescription medication for the management of pain within 30 days prior to the Screening and Baseline Visit
- 17. Currently taking opioid medication whether episodically or daily, within 30 days prior to the Screening and Baseline Visit.
- 18. Patients sensitive to Latex
- 19. If planning to become pregnant, pregnant or breastfeeding.
- 20. Anything that, in the opinion of the investigator, would place the participant at increased risk or impede the participant's full compliance with or completion of the study.

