7.2 Screening and Baseline Visit (Visit 0, 4 weeks period)

This visit will happen with 2 weeks after pre-screening. Participants will start the baseline period that will consist of 4 weeks.

- Obtain and document consent from subject participation in the study.
- Obtain signed Health Insurance Portability and Accountability Act (HIPAA)

Authorization

- Review medical/dental history to determine eligibility based on inclusion/exclusion criteria.
- Take blood pressure and collect weight and height.
- Review medications history to determine eligibility based on inclusion/exclusion criteria.
 - Record concomitant medications and therapies
- Perform QST examination
- Perform EEG
- Collect blood for Cytokine release assay

- - Perform urine pregnancy test (in women with childbearing potential)
 - Provide instruction to complete 4 outcome measure questionnaires in paper or electronically for review next visit
 - Provide instruction to complete Daily Symptom Diaries electronically or in paper dispense forms.

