7.3.1 First treatment cycle (Visit 1, Day 0)

- Review Daily Symptom Diaries in eCRF or collect and review it in paper forms
- Review medical/dental history to determine eligibility based on inclusion/exclusion criteria.
- Record concomitant medications and therapies
- Take blood pressure and collect weight
- Assess and record adverse events (AEs)
- Perform urine pregnancy test (in women of childbearing potential)
- Review 4 questionnaires from Visit 0 in eCRF or collect and review the paper forms

- Provide instruction to complete 4 new outcome measure questionnaires in paper or electronically for review at Visit 2.
- Provide instruction to complete Daily Symptom Diaries electronically or provide them in paper forms
- Deliver the injection of the study drug or placebo
- Schedule next visit

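### Three sections say that drugs which slow the gut are excluded, but none of the 20 exclusion criteria in section 5.2 says so

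*Combined protocol and SAP*

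**What the plan says.** Section 2.3.1 describes serious constipation in patients prescribed erenumab and adds: "In some cases, hospitalization or surgery was required". It then answers that risk at entry: "Constipation and the use of medications that decrease gastric motility are in our exclusion criteria". Section 9.3.2 repeats that statement. Section 6.3 makes the same claim and points the reader to the list: "Exclusion criteria includes medical history of constipation or taking medications associated with decrease of G.I motility as well as pre-existent hypertension (See 5.2".

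In section 5.2 the only criterion about the gut is number 3, which names conditions: "Participants with high blood pressure, uncontrolled high blood pressure, malignant disease, chronic constipation, any malabsorption disorders such as IBSc". Criterion 17 excludes one drug class: "Currently taking opioid medication whether episodically or daily, within 30 days prior to the Screening and Baseline Visit". Criterion 20 is a general clause: "Anything that, in the opinion of the investigator, would place the participant at increased risk".

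Section 7.2 (Visit 0) requires staff to "Review medications history to determine eligibility based on inclusion/exclusion criteria". At Visit 1, when the first dose is given, section 7.3.1 requires staff to "Review medical/dental history to determine eligibility based on inclusion/exclusion criteria", while medications are only recorded.

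**The concern.** A reader of the risk section is told that patients on motility-reducing drugs cannot enter. The section cited for that rule does not contain it. If screening follows section 5.2, such a patient can be randomized and dosed without any listed criterion being broken.

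What is at stake is participant safety at entry and the accuracy of what the IRB and DSMB are told, since either may credit a safeguard that the criteria lack. The protocol does have later protections: the symptom inventory, the telephone calls between visits, and withdrawal on new-onset constipation. These act after dosing, so they do not replace an entry rule.

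**Working it through.** No arithmetic beyond counting applies. The check sets the sections side by side.

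**1. Where the exclusion is declared.** Sections 2.3.1, 6.3 and 9.3.2, so three places. Sections 2.3.1 and 9.3.2 speak of gastric motility and section 6.3 of GI motility; the difference does not matter here.

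**2. Whether section 5.2 contains it.** The criteria run from 1 to 20 with no number missing, so redaction or text extraction does not explain the gap. Five of the 20 concern medication or treatment use:

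| Criterion | Subject | Covers motility-reducing drugs? |
|---|---|---|
| 9 | Anti-CGRP antibodies (past or current), current gepants | No |
| 11 | Drugs for trigeminal neuropathic pain with a dose change in the three weeks before baseline | No; a stable dose passes |
| 15 | Investigational treatment in the previous 30 days | No |
| 16 | New daily pain prescription in the previous 30 days | No; an established one passes |
| 17 | Opioids | Only as far as opioids count as such drugs |

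The other 20 − 5 = 15 concern conditions, substance abuse, imaging findings, sensitivities, pregnancy or general judgement. The count of criteria that state the exclusion is 0 of 20. Of the five medication criteria, at most one overlaps with it.

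**3. Whether other references to section 5.2 resolve.** Hypertension, in the same sentence of section 6.3, is in criterion 3. Latex sensitivity, cited from section 6.2, is criterion 18. The motility rule has no counterpart, which points to an omission from the list rather than to loose summarizing.

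**4. Whether another section fills the gap.** The inclusion criteria do not state the rule, and neither do section 6.6 or Appendix B. Section 6.6.4 bars starting several drug classes, or using them as rescue, during the study; it does not bar continuing one. Inclusion criterion 6 and section 6.6.1.1 keep participants on an existing daily pain prescription. No section says which drugs count as motility-reducing.

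**5. How screening works.** Section 5.4.1 bases enrollment on the inclusion and exclusion criteria. Visit 0 is the only visit whose procedure list checks medication history against them. Appendix A marks the eligibility review only at pre-screening and Visit 0. Section 5.5.1 allows withdrawal when an exclusion criterion is met later or recognized late, and that too depends on what the criteria contain.

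**6. Constipation itself.** Section 6.3 refers to a history of constipation, sections 2.3.1 and 9.3.2 to constipation without qualification, and criterion 3 to chronic constipation. A patient with a past, non-chronic episode is excluded on the wording of section 6.3 but not on that of criterion 3.

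**The case against.** The best case for the protocol is that its intent is plain. The exclusion is declared three times and contradicted nowhere. Section 7.2 refers to the inclusion and exclusion criteria without limiting them to section 5.2, so a careful investigator could treat the declarations as binding. Criterion 20, read with sections 2.3.1 and 6.3, steers that investigator toward exclusion, and criteria 2 and 3 carry similar judgement wording. Chronic constipation and opioids are already excluded, medications are recorded at every visit, and a single center limits inconsistent application.

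Much of this stands as mitigation. It is fair to say that the check may be missed, not that it will be. It does not remove the inconsistency: section 5.2 is the list of exclusion criteria, section 6.3 itself defers to it, and discretion permits exclusion without requiring it.

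A second objection also has force. The documents never say which drugs slow the gut, nor that opioids or the pain prescriptions continued under inclusion criterion 6 are among them. The omission is therefore documented, but the size of the exposure is not. The point about continued pain prescriptions matters only if a class used for this pain is named.

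**Conclusion.** The concern holds; the eligibility list is wrong as written. An exclusion declared in three sections appears in 0 of the 20 criteria, so section 5.2 can admit patients whom the protocol says it excludes. It should be corrected.

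The conclusion rests on section 5.2 being the operative list, as its title and the cross-reference in section 6.3 indicate. Crediting criterion 17 as partial cover assumes that opioids count as motility-reducing drugs; without that assumption, no medication criterion overlaps. The number of participants affected cannot be derived from the documents. Section 6.3 reports the identified adverse reactions, constipation among them, at below 5% in clinical trials, but gives no rate for patients taking such drugs. The primary endpoint, power and analysis are not in question.

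**What to change.** - Add a numbered criterion to section 5.2 excluding current use of medications that decrease GI motility. The investigator and the medical monitor should name the drug classes and set a look-back window.
- Use one constipation wording in sections 2.3.1, 5.2, 6.3 and 9.3.2.
- State the exception in inclusion criterion 6 and section 6.6.1.1, so that a daily pain prescription in a named class is not carried into the study.
- Add one line to the Visit 0 medication review.
- If the investigators decide not to exclude these drugs, delete the statement from sections 2.3.1, 6.3 and 9.3.2 instead.

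The cost is one wording amendment, which section 15.2 says needs approval from AMGEN and the IRB. The downside is a possibly smaller eligible pool, depending on the classes named. Section 5 already expects 200 screened for 40 enrolled, or 200/40 = 5 per participant, and naming a class often used for this pain would raise that load.
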